#### **Assessment of Treatment Outcome and Time Course.**

Primary Measures: (1) Binge-eating frequency (EDE); (2) weight (measured weight and height and BMI); for Stage 2 LDX vs Placebo test: "Relapse" to DSM-5 threshold of once-weekly binge eating on EDE

Secondary Measures: (1) "remission" (zero binges past 28 days on EDE; eating disorder pathology (EDE global), depression (BDI-II); for exploration of mediators: (2) eating behaviors (EDE, TFEQ, FCI-II), executive control and impulsivity (BIS-11, DDT, Trails) and selected metabolic measures (lipid profiles, HbA1c, blood pressure, HR) to characterize metabolic outcomes and allow comparison with RCTs for LDX and NB.

**Figure 2.** Grid depicting when each measurement is obtained

Assessment Points	BASELINE (2 MTG)	DURING RX STAGE 1 1-MONTH	DURING RX STAGE 1 2-MONTH	POST RX STAGE 1 3-MONTH	DURING RX STAGE 2 4-MONTH	DURING RX STAGE 2 5-MONTH	POST RX STAGE 2 6-MONTH	6 AND 12- MO FOLLOW- UP (18 MONTH TOTAL)
MINI Psychiatric Interview, Height, Credibility,	•							
EDE Interview, SF-12, GPAQ, Lipid Profile, HbA1C, Glucose	•			•			•	•
EDE-Q-I, BDI-II, GLTEQ, Weight, BP, HR	•	•	•	•	•	•	•	•
TFEQ-Restraint	•	•		•			•	•
DDT	•	•		•			•	
FCI-II, PFS	•	•		•	•		•	
BIS-11	•	•		•	•		•	•
ELOCS	•	•		•				
Trails, YFAS, BRS, Amphetamine Testing	•			•			•	
Placebo Ratings					•		•	
Start of New Treatments				•			•	•
Medical History Creatinine w/ EGFR PSQI	•			•				
Adverse Events		•	•	•	•	•	•	
Insulin	•			•				

Liver Function	•			•	• (Non- responde rs only)			
Pregnancy Test	•			•				

**Clinical Assessments:**

- MINI International Neuropsychiatric Interview-Version 7.0 (MINI) (Sheehan et al., 2014) is a brief structured interview for Axis I psychiatric disorders. Validation and reliability studies have supported the MINI, including good convergence with SCID (Sheehan et al 2014). The MINI requires much less time than the SCID and reduces subject burden while providing adequate psychiatric data to characterize patients and determine exclusion criteria. We will use the MINI-7 (based on *DSM-5*).
- Eating Disorder Examination Interview–16th Edition (EDE); Fairburn & Cooper, 2008) investigator-based interview assesses the features of eating disorders and diagnoses. The EDE will be our primary assessment method for binge eating and ED pathology at baseline, post-treatment(s), and follow-ups. EDE focuses on past 28 days, except for diagnostic items (rated for durations stipulated in *DSM-5*). EDE assesses frequency of different forms of overeating, including objective bulimic episodes (OBE) (binge eating, i.e., unusually large amounts of food with loss of control). EDE also comprises four scales (restraint, eating concerns, weight concern, and shape concern) and a global severity score. EDE has good psychometric properties ([name] et al., 2001a, 2001b), is the major outcome measure for BED RCTs (Wilfley et al., 2002; Wilson, Wilfley, et al. 2010), and has good test-retest reliability in obese and BED groups ([name] et al, 2004, 2005).
- Trail Making Test, Parts A & B (Trails). Trails is a measure of executive attention and relevant to LDX models (Kessler et al., 2016). In Part A, participants connect numbered dots consecutively as quickly as they can and In Part B, participants connect dots labeled with numbers and letters, alternating between number and letter. Trails can be administered in <5 minutes (Gaudino et al., 1995; Strauss, Sherman, & Spreen, 2006).
- We will also gather clinical data on the patient's medical history prior to the study, which we will update as indicated in Figure 2. If patients begin other treatments, this will allow us to account for this in analyses.

**Self-Report Questionnaires:**

- EDE-Questionnaire Version with Instructions (EDE-Q-I); Fairburn & Beglin 1994; Celio, Wilfley et al. 2004) generates the same eating data and scale scores as EDE interview, has good test-retest reliability with BED ([name], Masheb et al. 2001; Reas, [name] et al. 2006). EDEQ will be used across all assessment points given its low burden (in addition to EDE at major assessment points). EDEQ converges well with EDE as a measure of "change" (Sysko, et al. 2005). In N=200 BED patients, alphas for the four scales ranged .71 to .75.
- Three Factor Eating Questionnaire (TFEQ); Stunkard & Messick, 1985) taps eating behaviors with 3 factors: cognitive restraint, disinhibition, and hunger; however, we will be using the restraint subscale for this study. TFEQ has validity (Foster et al., 1998), and shows differential response across treatments consistent with putative CBT mechanisms (Blomquist & [name], 2011; [name] & Masheb, 2005; Safer et al., 2004). In N=200 BED patients, alphas for the 3 scales ranged .67 to .76.
- Food Craving Inventory (FCI-II); White et al., 2002) assesses general and specific food cravings (relevant for NB) and comprises 4 subscales for different food groups. FCI-II is validated and

psychometrically supported in studies with obese and with BED groups (White et al., 2002; White & [name], 2005). Internal consistency was 0.93 for total score and ranged 0.70-0.85 for subscale items in N=464 BED patients.

- The Power of Food Scale (PFS) (Lowe et al., 2009) assesses psychological impact of and drive to eat palatable foods. PFS measures appetite for – rather than consumption of – palatable foods. PFS has been validated in normative (Lowe et al., 2009) and treatment-seeking obese patients (Cappelleri et al., 2009). PFS comprises 3 scales reflecting food proximity (food available, food present, and food tasted) supported by factor analysis and good test-retest reliability and internal consistency (range 0.81-0.91) (Cappelleri et al., 2009). The PFS is a good measure of the hedonic impact of food environment cues; fMRI studies have reported associations with state cravings for desired foods and shifts in brain networks (Rejeski et al., 2012).
- Eating Loss of Control Scale (ELOCS) (Blomquist et al., 2014) assesses the complexity of loss of control eating over the past four weeks. The ELOCS has demonstrated good convergent validity and is considered a valid self-report questionnaire that may provide important clinical information regarding experiences of loss-of-control eating in persons with obesity and BED.
- Godin Leisure Time Exercise Questionnaire (GLTEQ) (Godin et al., 1985) assesses mild, moderate, and vigorous physical activity, has good test-retest reliability (Jacobs et al., 1993) and has been validated using various activity measurement methods (Miller et al., 1994).
- Global Physical Activity Questionnaire (GPAQ) (Armstrong et al., 2006) is recommended by the NIH ADOPT guidelines for the assessment of physical activity and sedentary behavior when actigraphy is not used (Lytle et al., 2018).
- Beck Depression Inventory (BDI-II) (Beck & Steer, 1987) 21-item version is a widely used measure of the symptoms of depression. A voluminous literature has documented good internal consistency (studies range .73 to .95), short-term test-retest reliability, and convergent validity (Beck, Steer, & Garbin, 1988). In a recent consecutive series of N=200 obese BED patients at Yale, alpha coefficient was .87.
- Barratt Impulsiveness Scale (BIS-11) (Patton et al., 1995). The BIS-11 is a well established and widely scale of impulsivity; BIS-11 yields three second-order factors: attentional (consisting of the first-order factors attention and cognitive instability), motor (consisting of the first-order factors motor and perseverance) and non-planning (comprised of the first-order factors self-control and cognitive complexity) (Patton et al., 1995). These measures are relevant to disordered eating and reward systems (Carver & White, 1994), neurobiology of BED (Balodis et al., 2013), and to models of BED and possible LDX effects (Kessler et al., 2016).
- Delayed-Discounting Task (DDT), related to impulsivity, occurs when individuals choose smaller, more immediate rewards over larger rewards that would occur after a time delay (Green & Myerson, 2004). Analysis of responses with varied time delays and varied rewards indicates individuals' selections fall into a hyperbola-shaped pattern balancing delay and size of rewards (Green & Myerson, 2004) including obesity (Thomas et al., 2015). Individuals with BED show steeper responses than participants with obesity (Manwaring et al., 2011). Kirby is a DDT that asks participants to choose between two hypothetical rewards, one of which is after a delay. Amount of the short-term reward, long term reward, and time delay vary across 27 items, allowing for the computation of a "discounting rate" (i.e., when participants do not have a preference between smaller immediate reward and the larger but delayed reward) fitted to a hyperbolic discount curve (Kirby, 2009). These discounting rates have shown evidence of stability over 5-week ( $r=.77$ ) and 57-week ( $r=.63$ ) test-retest periods. DDT is relevant to neurobiologic models of BED (Balodis, [name], & Potenza, 2015) and models of LDX (Kessler et al., 2015).

- Short-Form-12 MOS Health Survey (SF-12); Ware & Sherbourne, 1992) taps health-related quality of life, with established reliability and validity (McHorney et al., 1993, 1994), and will be used to calculate quality-adjusted life years (**QALY**) per established methods (Revicki et al., 2005; Tsai et al., 2005) used in recent BED research on cost-effectiveness of LDX (Agh et al., 2016) and CBTgsh (Lynch et al., 2010; Dickerson, 2011).
- The Yale Food Addiction Scale 2.0 (YFAS 2.0 and YFAS-S 2.0) (Gearhardt et al., 2016) is a self-report questionnaire that adapted the 11 symptoms of substance dependence (as listed in the DSM-5) to assess addictive-type eating behaviors.
- Pittsburgh Sleep Quality Index (PSQI) is a widely used 19-item self-report measure which assesses sleep quality during the prior month (Buysse et al., 1989). The PSQI generates a global score ranging from 0 to 21; scores greater than five are indicative of poor sleep quality.
- Brief Resilience Scale is a psychometrically-sound brief measure assessing a person's ability to thrive and recover from stress.

#### Physical Assessment:

- Pregnancy test: All women of reproductive age who are sexually active will be required to have a pregnancy test before Stage 1 randomization. Women of reproductive age who are sexually active who are randomized to Stage 1 medication groups (CBT+ LDX or LDX ONLY) will also require a pregnancy test before Stage 2 treatment.
- Lipid profiles will be obtained following established protocols (12-hr overnight fast, no exercise for 48 hr, a.m. draw) (Anderson et al., 1995).
- Glycemic Control will be determined with **HbA1c**, a routine measure of average glucose control for a previous (3-month) period.
- Hepatic function panel (Liver Function) will be assessed for safety.
- Creatinine w/ EGFR (Renal Function) will be assessed for safety.
- Glucose, Mean Plasma Glucose, and Insulin levels will be obtained.
- Thyroid-stimulating hormone (TSH) will be assessed if patients report any history of thyroid disease or are taking thyroid medications.
- Body weight measured (no shoes) on high-capacity equilibrated digital scales and height measured on stadiometer to nearest 0.1 cm will be used to calculate BMI ( $\text{kg} \cdot \text{m}^{-2}$ ). Weight will be measured at all assessment points and will also be measured every two weeks throughout treatments.
- Blood Pressure (BP) and Heart Rate (HR). BP readings (systolic and diastolic) and HR will be obtained regularly at clinic meetings.
- Urine drug testing: For non-responders in Stage 2 (those eligible for the NB versus placebo arm), participants will receive urine drug testing for opiates.

#### Perceptions of Treatment:

- Treatment Credibility ratings will be examined before beginning each stage of treatment.
- Placebo/Med Ratings Patients and clinicians will provide *medication versus placebo ratings*.
- Treatment Compliance for CBT will include session attendance and self-monitoring compliance and counts. Compliance for medication treatment(s) will include pill count method and will be supplemented by additional "objective" method. Medication compliance with LDX will be monitored through evaluation of urine levels of amphetamine. In addition, we will be able to explore the relationships between compliance for CBT and LDX with the primary outcomes.
- Adverse Events will be collected during clinic visits using standard adverse event checklists of commonly reported adverse events for the **LDX** and the **NB** medications. Research-clinicians will ask open-ended and follow-up questions as needed.

5. Genetic Testing N/A 

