**LDX Pharmacotherapy Treatment Protocol.** Medication will be double-blind; patients and study staff, physicians and investigators will be blind to medication assignment. **LDX, FDA-approved for BED**, will be prescribed per procedures found to be superior to placebo in two large-scale phase 3 RCTs (McElroy et al., 2015). The LDX (dose-optimization at 50-70mg per day) protocol followed the McElroy et al (2015) RCT findings that 50-70mg/day dosing was significantly superior to 30mg/dosing and to placebo.

During week 1, LDX will be 30 mg/day for initial titration. During week 2, LDX will be titrated to 50mg/day. During weeks 3-4, LDX increases to 70mg will be made based on acceptable tolerability and clinical need. If 70mg is not tolerated, downward titration to 50mg/day can occur. For the remaining treatment (weeks 4-12), the optimized LDX dose (50 or 70 mg/day) will be maintained.

For the Stage 2 randomized maintenance (double-blind) treatment, a similar approach to dose-optimization will be followed for responders. "Responders" re-randomized to LDX will continue taking LDX at the same dose as Stage 1. "Responders" randomized to placebo will be switched from LDX to placebo. Participants will be instructed to take the medication (active or placebo) once daily in the morning.

Safety and tolerability will be assessed during study clinic visits as will clinical compliance with the study medication. During the dose-optimization period, if the patient develops tolerability concerns, dosing can be reduced once to achieve tolerability. If the patient cannot tolerate the medication, has adverse effects, or is non-compliant with medication for > 7 consecutive days, s/he will be discontinued from the medication arm. Physician visits will be brief (10-15 minutes) and focus on compliance with dosing and evaluating side effects without integrating dietary, behavioral, or CBT techniques.

In Stage 1 or Stage 2, participants taking medication for greater than 4 weeks, a taper will be provided (Refer to Minimizing Risk section on page 20 for details).

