**LDX:** Effective screening will exclude all prospective participants who would be at greater risk for complications because of medical or psychiatric illnesses. LDX is classified as a DEA-controlled substance and product labeling includes a "Warning" that CNS stimulants have high potential for abuse/dependence. Thus, potential participants with a history of drug and alcohol problems will be excluded and all participants in the RCT will be evaluated carefully at all clinic visits for any signs of medication misuse in addition to structured assessments of potential side-effect or adverse events per the published procedures (McElroy et al., 2015). The LDX pharmacologic treatment protocol follows the evidence-based dose-optimization protocol that has demonstrated safety, tolerability, and efficacy in the same patient group during the 12-week duration of treatment. Subjects will be evaluated repeatedly throughout the study and will be monitored for any signs of medication misuse and for side-effects and adverse reactions using structured assessments at all clinic visits. If any participant experiences adverse reactions, or if side effects are too severe, the medication will be discontinued. Regarding the risk of serotonin syndrome, all SSRI medication and strong inhibitors of CYP2D6 will be excluded for this study. Regarding risk of heart complications, individuals with a history of cardiac disease will be excluded. Participants will be required to have an EKG before enrolling. Subjects with a baseline EKG that is assessed and determined to be indicative of one of the cardiac disorders listed in the exclusion criteria will be excluded. Regarding psychiatric symptoms, such as mania and psychosis: At monthly follow-ups during Stage 1 and Stage 2, study clinicians will assess manic and psychotic symptoms using structured questions from the Mini International Neuropsychiatric Interview (MINI), a well-established interview used to assess psychiatric disorders. This added specific assessment will be conducted with

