**Measurement and reporting of adverse events.**

Adverse event data will be collected on an on-going basis. These data will be collected and examined with blindness to the medication conditions. Adverse events data will be reviewed by the PI, co-investigators, and the safety officer throughout this trial (see Table below). A summary of adverse events will be provided to the Yale IRB yearly during the annual renewal review process. Any serious or unanticipated adverse events will be reported to the NIH and to the Yale IRB within 48 hours.

The frequency of data review is summarized in the following table:

Table	Data type	Frequency of Review by PIs and Research Team	Frequency of Review by PI and DSMB
Table 1	Subject accrual	Monthly	Twice Yearly
Table 2	Treatment completion rates (retention/attrition)	Twice Yearly	Twice Yearly
Table 3	Adverse and serious adverse event rates	Twice Yearly	Twice Yearly
Table 4	Checklist for DSMB	NA	Twice Yearly

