Participation rates (retention and attrition) will be reviewed on an ongoing basis by the PIs and co-investigators to identify any potential problems, and formally by the PIs and DSMB twice-yearly. Any differential dropout across blinded study groups and/or higher than expected dropout will be reviewed by the investigators to determine whether any problems are present and what, if any, corrective action needs to be taken.

During the reviews, if the DSMB has concerns about whether attrition has reached a level that might inhibit the ability of the study to address its primary aims, they will suggest a meeting to discuss methods for improving subject retention. Previous pharmacotherapy studies for BED (with comparable time frames for pharmacotherapy) have reported attrition rates between 20% and 38%. Studies of NB for obesity treatment reported attrition of 30% to 45%. Thus, "trigger points" for review and discussion by principal investigator and research staff will be: 35% ("low alert"), 40% ("mid alert"), 45% ("high alert"), 50% ("extreme alert"). With early alerts to problems, action would be taken to avoid higher level alerts; if a higher level alert should arise, more drastic actions would be taken.

Trial Stopping Rules

Given that this study is deemed greater than minimal risk to human subjects, it is more likely that attrition or difficulty in recruiting adequate numbers of participants will require stopping the trial than would excess adverse events. However, as outlined, adverse events will be monitored in all participants, and the safety officer, together with the PI, will alert the Yale IRB and the NIH if a larger (or more serious) than reasonably expected adverse event rate should occur. Other potential issues relating to stopping rules for this trial include:

1. New Information

It is unlikely that any new information will become available during this trial that would necessitate stopping the trial. If new safety data (i.e., pertaining to short-term use of the study medication) become available, this will be evaluated.

2. Limits of Assumptions

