**Risks.** LDX is classified as a DEA-controlled substance and product labeling includes a “Warning” that CNS stimulants have high potential for abuse/dependence. Thus, as previously mentioned, potential participants with a history of drug and alcohol problems will be excluded and all participants in the RCT will be evaluated carefully at all clinic visits for any signs of medication misuse in addition to structured assessments of potential side-effect or adverse events per the published procedures (McElroy et al., 2015). Research has found that 9% of patients reported treatment emergent side-effects resulting in medicine discontinuation (Gasior et al., 2017). In addition, the following side effects were reported in adults with BED taking LDX and at least twice as often as the placebo: dry mouth (36%), insomnia (20%), decreased appetite (8%), increased heart rate (7%), feeling jittery (6%), constipation (6%), anxiety (5%), diarrhea (4%), decreased weight (4%), hyperhidrosis (4%), and the following side effects occurred at 2% (vomiting, gastroenteritis, paresthesia, pruritis, upper abdominal pain, energy increased, urinary tract infection, nightmare, restlessness, and oropharyngeal pain).

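### No adverse-event checklist is scheduled before treatment and no rule limits events to new or worsened symptoms, so symptoms present at entry may be recorded as adverse events

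*Combined protocol and SAP*

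**What the plan says.** Under Perceptions of Treatment (section 4, Research Plan), "Adverse Events will be collected during clinic visits using standard adverse event checklists of commonly reported adverse events" for the two medications, and "Research-clinicians will ask open-ended and follow-up questions as needed". In Figure 2 the "Adverse Events" row is marked at months 1, 2, 3, 4, 5 and 6, and the baseline cell is empty.

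Other sections describe collection more broadly. Section 11 (Minimizing Risks, LDX) has participants monitored for "side-effects and adverse reactions using structured assessments at all clinic visits". The LDX treatment protocol says "Safety and tolerability will be assessed during study clinic visits as will clinical compliance with the study medication". The Data and Safety Monitoring Plan says "Adverse event data will be collected on an on-going basis" and asks for a five-level attribution, from definite to unrelated.

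The event rates are put to use. Under Trial Stopping Rules, the safety officer and the PI "will alert the Yale IRB and the NIH if a larger (or more serious) than reasonably expected adverse event rate should occur". The monitoring plan also provides for early reporting when events are more frequent than expected, and has the investigators weigh event frequency when deciding on protocol or consent changes. It gives no numerical threshold.

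**The concern.** A prompted checklist picks up whatever the participant has, whether or not treatment caused it. Several listed items are everyday complaints. Without a pre-treatment answer to the same checklist, an item ticked on treatment cannot be told from one that would have been ticked at entry, except by asking the participant to remember. The plan also has no counting rule that would make the distinction matter.

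Two things are at stake: the absolute rates that go into the safety reviews, and the descriptive comparison of LDX with CBT at the end of Stage 1. Reports to the DSMB are aggregate and no preliminary safety analysis by arm is proposed, so during the trial background symptoms cannot be subtracted by looking at the CBT arm. A missing pre-treatment reading cannot be recovered later.

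**Working it through.** **Schedule.** The empty baseline cell does not look like a table-reading fault: neighbouring rows fall where they should (placebo ratings only in Stage 2 columns; BDI-II, blood pressure and heart rate at baseline and after). The passages on clinic visits and on-going collection allow recording before month 1, but all concern participants already on treatment. None supplies a pre-treatment checklist.

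**What already has a baseline.** PSQI (sleep), BDI-II (mood), blood pressure, heart rate and medical history. Section 11 already judges heart rate as a rise from baseline. That leaves mainly dry mouth, jitteriness, constipation and diarrhea (LDX list, Section II, Risks), and headache and nausea (NB list).

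**Size.** The plan gives no figure to reproduce, so this is an illustration.

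- *e*: rate at which a symptom appears or worsens on treatment. For dry mouth on LDX, 36% (Section II, LDX Risks).
- Comparator *e*: that section says "the following side effects were reported in adults with BED taking LDX and at least twice as often as the placebo", so 18% is the highest placebo rate it implies. Using it for CBT is an assumption, since Stage 1 has no placebo.
- *b*: share with the symptom at entry. Not in the documents; assumed 5–40%, equal across arms by randomization and unrelated to *e*.
- Worst-case counting: every symptom present at entry is recorded as an event.

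Recorded rate = *b* + (1 − *b*)·*e*, so the recorded difference = (1 − *b*)·(*e*₁ − *e*₀).

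At *b* = 10%: 0.10 + 0.90 × 0.36 = 0.424 and 0.10 + 0.90 × 0.18 = 0.262.

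| *b* (assumed) | LDX | Comparator | Difference (points) | Ratio |
|---|---|---|---|---|
| 0 | 36.0% | 18.0% | 18.0 | 2.00 |
| 5% | 39.2% | 22.1% | 17.1 | 1.77 |
| 10% | 42.4% | 26.2% | 16.2 | 1.62 |
| 20% | 48.8% | 34.4% | 14.4 | 1.42 |
| 40% | 61.6% | 50.8% | 10.8 | 1.21 |

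If the comparator rate were 9% (assumed, half the bound), the difference would still shrink by (1 − *b*): 27.0 points at *b* = 0, then 0.90 × 27.0 = 24.3 at 10% and 0.80 × 27.0 = 21.6 at 20%.

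**A limit on the second result.** The shrinkage is relative to a count of new or worsened symptoms, with *e* the same whether or not the symptom was present at entry. If existing symptoms never worsened and everyone stayed in the denominator, a new-onset count at *b* = 10% would be 0.90 × 36% = 32.4% versus 0.90 × 18% = 16.2%. The difference, 16.2 points, then equals the recorded one; only the ratio (2.00 against 1.62) and the absolute rates are distorted.

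**The case against.** The strongest reply is that the plan has safeguards: clinicians can ask when a symptom began, and attribution allows an event to be called unlikely or unrelated. That stands in part. The documents never say that existing symptoms are counted, so a reader who infers that they are goes further than the text; the table is a worst case. But attribution is a causality judgement, and without an earlier answer it rests on recall.

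Other stronger readings are tempting and not supported:

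- **Nothing is collected before month 1.** This is true of the grid only; the text allows earlier collection on treatment.
- **The trial loses power to detect LDX side effects.** Section 13 plans no between-arm adverse-event test, so no power is lost. Only descriptive reporting is affected.
- **The safety alert would fire without a true excess.** The plan names no reference rates or threshold, and does not say whether its cited rates count new-onset events only. If they include background symptoms, part or all of the apparent excess disappears.
- **Insomnia is equally exposed.** PSQI at baseline and month 3 partly covers it.
- **Stage 2 has the same gap.** Figure 2 already has a month-3 checklist. What is missing is a statement that it is the reference. Everyone randomized in Stage 2 has taken LDX, so it is an end-of-LDX reading and an imperfect reference for NB, which starts one week after LDX stops.

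**Conclusion.** The point holds as a modest design gap. No checklist is scheduled before treatment, and no rule limits events to new or worsened symptoms. For any prevalence above zero, recording existing symptoms pushes reported rates above the new-or-worsened rates and pulls the LDX to CBT ratio toward 1. Under the model above, it also shrinks the difference by (1 − *b*).

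At an assumed 10–20% prevalence and an assumed 18% comparator rate, dry mouth would read 42–49% versus 26–34% instead of 36% versus 18%. These figures rest on a prevalence the documents do not give, a placebo bound standing in for CBT, the cited 36% taken as a new-or-worsened rate, and every existing symptom being recorded. The true size cannot be fixed from the documents, and no planned test is affected. The change is worth making because it is cheap and the missing reading is irrecoverable.

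**What to change.** 1. In Figure 2, mark the adverse-event checklist at baseline, before the first dose or session, in all three arms.
2. Under Perceptions of Treatment, state that a checklist item is reported as an adverse event when it is new or worse than that reading.
3. Name the existing month-3 checklist as the Stage 2 reference, and note that for LDX-treated participants it is an end-of-LDX reading.

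While editing, align the monthly grid with the passages on clinic visits and on-going collection.

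Cost: a few minutes at a baseline visit already held, and two or three sentences of text.
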